6.2.8.1.1. Conditions Not Requiring KPT-9274 Dose Reduction

The following conditions are exceptions to the dose-modification guidelines. KPT-9274 does not need to be held in the following cases:

- Alopecia of any grade.
- Electrolyte or serum analyte (e.g., urate) abnormalities that are reversible with standard interventions.

6.2.8.1.2. Dose Holds or Reductions for Nivolumab (Part C)

- Dose reductions are not allowed for nivolumab. Consult the product label for dose holds.

6.2.9. Missed or Vomited Doses

6.2.9.1. Missed Doses of Study Treatments

If a dose must be skipped (e.g., due to recommendation of Investigator), the next dose will be taken as per schedule; all missed doses should be documented.

6.2.9.2. Vomited Doses of Study Treatments

If a dose is vomited within 1 hour of ingestion, it will be replaced. If vomiting occurs more than 1 hour after dosing, it will be considered a complete dose.

6.3. Study Treatment Storage

Study treatments must be received by designated personnel at the study site, handled and stored safely and properly, and kept in a secured location to which only the investigator and designated site personnel have access. Upon receipt, KPT-9274 and niacin ER should be stored according to the instructions specified on the drug labels and in the IB for KPT-9274. Nivolumab should be stored according to the package label.

6.4. Study Treatment Accountability

The Investigator or designee must maintain an accurate record of the shipment and dispensing of study treatment in a drug accountability log. Study treatment accountability will be noted by the clinical research associate during site visits and at the completion of the study. Patients will be asked to return all unused study treatment and packaging on a regular basis, at the end of the study or at the time of study treatment discontinuation.

KPT-9274 should not be used for any purpose outside the scope of this protocol, nor may KPT-9274 be transferred or licensed to any party not participating in the clinical study.

6.5. Selection and Timing of Dose for Each Patient

The rationale for the dose to be used is provided in Section 1.3.1. Guidelines for modifying the dose of KPT-9274, if needed due to AEs, are given in [Table 16](#).

6.6. Method of Assigning Patients to Treatment Groups

During the Dose Escalation Phase, assignment of a patient to a particular cohort will be coordinated by Karyopharm. Patients will be enrolled in the Dose Expansion Phase based on Investigator judgment and availability within the cohort. Patients may be enrolled in any actively enrolling cohort.

6.7. Blinding

Not applicable, this is an open-label study.

6.8. Compliance

The Investigator or other study staff will either directly administer or supervise study treatment given in the clinic and instruct the patient on study medication self-administration, as appropriate. Patients will be provided with a take home diary to complete on home dosing days; the patient diary will be reviewed at each clinic visit.

Patients will be asked to bring their study medication containers with them at each visit and compliance with protocol-defined study treatment intake will be checked by tablet count.

Compliance to study medication will be assessed by the Investigator at each visit and recorded in source documents after discussion with the patient and performing drug accountability. Dates will be recorded as per study treatment schedule. The Investigator will account for the number of tablets dispensed against those returned by the patient. Any deviations and missed doses will be recorded in the eCRF.

The Investigator will try to ensure complete compliance with the dosing schedule by providing timely instructions to the patients. In case of non-compliance, the patients will be instructed again.

6.9. Supportive Care, Contraception Requirements, and Concomitant Medications

6.9.1. Supportive Care

Patients are expected to be aggressively treated to minimize the likelihood and/or severity of side effects at the discretion of the Investigator (consultation with the Karyopharm Medical Monitor is strongly encouraged), including hematologic and musculoskeletal (arthralgias and myalgias) symptoms observed in humans.

Supportive care including anti-nausea/anti-emetic therapy, acid suppression (e.g., PPIs \pm H2 blockers), anti-diarrheal therapy, and other standard treatments may be administered as per institutional guidelines for symptomatic patients. For additional options, please see NCCN Supportive Care Clinical Practice Guidelines in Oncology. Note: the use of PPIs is allowed in all patients but the Investigator must consult with the Karyopharm Medical Monitor prior to their use in patients receiving niacin ER. If any deficiencies in vitamin B12, folate, iron, erythropoietin, or transferrin are observed, then standard medical practice for their replacement should be instituted.

Anemia appears to be dose dependent and should be treated with dose interruption, dose reduction, use of growth factors (i.e., erythropoietins), and/or transfusions. The addition of niacin ER (up to 2,000 mg daily dose, per label) will be allowed after completion of the DLT period in cycle 1 (first 28 days) in an attempt to offset potential side effect (i.e. anemia, arthralgias, myalgias, etc.) of KPT-9274. After Week 8, niacin may be titrated, as per label, to patient response and tolerance. If response to 1000 mg daily is inadequate, increase dose to 1500 mg daily; may subsequently increase dose to 2000 mg daily. Daily dose should not be increased more than 500 mg in a 4-week period, and doses above 2000 mg daily are not recommended. Women may respond at lower doses than men.

Arthralgia should be treated with non-steroidal anti-inflammatory drug (NSAIDs), cyclooxygenase-2 (COX-2) inhibitors, acetaminophen, tramadol, and/or low-dose steroids. Myalgia and flu-like illness should be treated with KPT-9274 dosing at night, acetaminophen (including pre-treatment with acetaminophen), NSAIDs, COX-2 inhibitors, and/or low-dose steroids. Consultation with the Karyopharm Medical Monitor is recommended for questions regarding these recommendations.

For additional information on supportive care recommendations for events such as anemia, arthralgias, and myalgias see the current version of the IB as well as Section [7.5.2](#) and Section [7.5.3](#).

6.9.2. Non-study Related Concomitant Medication and Treatment

No significant inhibition of any of the CYP450 enzymes were observed after KPT-9274 treatment. Weak induction of CYPs 1A2, 2B6, and 3A4 were observed in an exploratory pre-clinical study after KPT-9274 treatment; however, it is unlikely that a potential drug-drug interaction will occur in a clinical setting. Therefore, the use of any concomitant medication/therapy (except medications listed in the prohibited medications section, see Section [6.9.3](#)), including over-the-counter (OTC) medications (excluding herbal supplements, dietary supplements), deemed necessary for the care of the patient is permitted during the study.

6.9.2.1. Permitted Concomitant Medication

Medications required to treat AEs, manage cancer symptoms, concurrent stable diseases and supportive care agents (e.g., blood product transfusions [see Section [6.9.2.6](#)], antibiotics with [if appropriate] granulocyte-colony stimulating factors [G-CSF] for neutropenic infection), pain medications, anti-emetics, and anti-diarrheals are allowed. Concurrent therapy with growth factors is allowed. The use of any immunosuppressive agents must be discussed between the Investigator and the Karyopharm Medical Monitor on a case-by-case basis. The addition of niacin ER (up to 2,000 mg daily dose, per label) is allowed after completion of the DLT period in cycle 1 (first 28 days) in an attempt to offset potential side effect (i.e. anemia, arthralgias, myalgias, etc.) of KPT-9274.

Note: the use of PPIs is allowed in all patients, but the Investigator must consult with the Karyopharm Medical Monitor prior to their use in patients receiving niacin ER.

Hormonal contraceptives are permitted in women of child-bearing potential. Hormonal contraceptives include any marketed contraceptive agent that includes an estrogen and/or a

progestational agent. Since the effect of KPT-9274 on oral contraceptives is unknown at this time, it is recommended that patients use at least 2 forms of contraceptives while on study.

Additionally, the nivolumab product label will be consulted to obtain the permitted concomitant medications for patients in Part C (the KPT-9274 + nivolumab).

6.9.2.2. Prevention of Pregnancy

Patients should not become pregnant or father a child while on this study because it is unknown whether KPT-9274 can affect an unborn baby. Women should not breastfeed a baby while on this study. It is important that patients understand the need to use birth control while on this study. Female patients of child-bearing potential must agree to use dual methods of contraception and have a negative serum pregnancy test at Screening; male patients must use an effective barrier method of contraception if sexually active with a female of child bearing potential.

The use of two forms of contraception are required, including one highly effective and one effective method of contraception, from the following lists.

- Highly effective methods include:
 - Hormonal contraceptives (e.g., combined oral contraceptives, patch, vaginal ring, injectables, and implants)
 - Intrauterine device (IUD) or intrauterine system (IUS)
 - Vasectomy and tubal ligation
- Effective methods include:
 - Barrier methods of contraception (e.g., male condom, female condom, cervical cap, diaphragm, contraceptive sponge)

Notes:

- *No barrier method by itself achieves a highly effective standard of contraception*
- *The proper use of diaphragm or cervical cap includes use of spermicide and is considered one barrier method.*
- *The cervical cap and contraceptive sponge are less effective in parous women.*
- *The use of spermicide alone is not considered a suitable barrier method for contraception.*
- *When used consistently and correctly, “double barrier” methods of contraception (e.g., male condom with diaphragm, male condom with cervical cap) can be used as an effective alternative to the highly effective contraception methods described above.*
- *Male and female condoms should not be used together as they can tear or become damaged.*

Acceptable methods of contraception also include:

- A sexual partner who is surgically sterilized or post-menopausal.
- Total (true) abstinence (when this is in line with the preferred and usual lifestyle of the patient), is an acceptable method of contraception. Periodic abstinence (e.g., calendar,

ovulation, symptothermal, post-ovulation methods) and withdrawal are not acceptable methods of contraception.

For both male and female patients, effective methods of contraception must be used throughout the study and for 3 months following the last dose.

See Section 1.2.2 for additional safety information related to pregnancy.

6.9.2.3. Radiation Therapy

Palliative radiation therapy to non-target lesions is permitted but study treatment should be held for ≥ 1 day before the start of palliative radiation therapy and ≥ 1 day following each dose of palliative radiation therapy. Treatment with KPT-9274 shall not be discontinued solely due to palliative radiation.

6.9.2.4. Hormone Ablation Therapy to Treat Advanced Prostate Cancer

Conventional hormone ablation therapy (HAT) is permitted while on study; however, patients receiving HAT prior to the start of the study must not terminate HAT within 6 weeks prior to C1D1; termination of HAT during this study must be discussed with the sponsor.

6.9.2.5. Glucocorticoid Therapy

Glucocorticoids ≥ 10 mg oral prednisone (or equivalent) per day are not permitted at baseline; however physiological doses ≤ 10 mg oral prednisone (or equivalent) for non-malignant conditions (e.g., asthma, IBD, etc.) are permitted as needed.

As part of supportive care (e.g., for nausea or anorexia), oral dexamethasone, up to 40 mg/week, may be given to patients.

6.9.2.6. Use of Blood Products

During treatment, patients may receive RBC or platelet transfusions per institutional guidelines. Patients who require repeated transfusion support should be discussed with the Karyopharm Medical Monitor.

Appropriate anti-coagulation is allowed during the study (e.g., low molecular weight heparin, direct factor Xa inhibitors, etc.). Warfarin is allowed during the study provided patients are monitored for international normalized ratio (INR) twice a week during the first 2 cycles of therapy, then weekly to biweekly thereafter.

Patients may receive supportive care with erythropoietin, darbepoetin, G-CSF or granulocyte macrophage-colony stimulating factor (GM-CSF), pegylated growth factors, and platelet stimulatory factors, in accordance with clinical practice or institutional guidelines prior to entry and throughout the study.

6.9.3. Prohibited Concomitant Medications

The use of niacin or niacin-containing supplements (e.g., multivitamins and energy drinks) is not allowed in cycle 1 of the Part A KPT-9274 only cohorts in the Dose Escalation or Expansion Phases. However, for patients in these cohorts that have cleared DLT in cycle 1, niacin ER (up to 2,000 mg co-administered with KPT-9274) may be used as supportive care in an attempt to

offset potential side effects (e.g. anemia, arthralgias, myalgias, etc.) of KPT-9274. Prior to initiating niacin ER, patient symptoms and laboratory values should be reviewed and discussed with the Medical Monitor for this study.

Investigational or commercial anticancer agents other than KPT-9274 are not allowed during the study. The initiation of any non-protocol specific anti-tumor treatment is considered an indication of disease relapse/progression and should be recorded appropriately in the eCRFs.

There are exceptions including localized palliative radiation (see Section [6.9.2.3](#)), hormonal contraception for the prevention of pregnancy (see Section [6.9.2.2](#)), hormonal therapy for patients with prostate cancer (see [Section 6.9.2.4](#)), and blood products/growth factors (see [Section 6.9.2.6](#)). For other possible cases, please consult the Karyopharm Medical Monitor.

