Patients are expected to be aggressively treated to minimize the likelihood and/or severity of side effects at the discretion of the Investigator (consultation with the Karyopharm Medical Monitor is strongly encouraged), particularly GI symptoms and hematopoietic toxicities as observed in KPT-9274 animal toxicology studies. Supportive care including anti-nausea/anti-emetic therapy, acid suppression (e.g., proton pump inhibitors [PPIs] ± H2-blockers), anti-diarrheal therapy, and other standard treatments may be administered as per institutional guidelines for symptomatic patients. For additional options, see NCCN Supportive Care Clinical Practice Guidelines in Oncology. Note: the use of PPIs is allowed in all patients, but the Investigator must consult with the Karyopharm Medical Monitor prior to their use in patients receiving niacin ER. Supportive care recommendations for events such as anemia, arthralgias, and myalgias include the following; (1) anemia: dose interruption, dose reduction, use of growth factors (i.e., erythropoietins), and transfusions; (2) arthralgia: non-steroidal anti-inflammatory drugs (NSAIDs), cyclooxygenase-2 (COX-2) inhibitors, acetaminophen, tramadol, and low-dose steroids; and (3) myalgia and flu-like illness: KPT-9274 dosing at night, acetaminophen (including pre-treatment with acetaminophen), NSAIDs, COX-2 inhibitors, and low-dose steroids. For patients in Part A, the addition of niacin ER (up to 2,000 mg daily dose, per label) is allowed after completion of the DLT period in cycle 1 (first 28 days) in an attempt to offset potential side effect (i.e. anemia, arthralgias, myalgias, etc.)

of KPT-9274. Consultation with the Karyopharm Medical Monitor is recommended for questions regarding these recommendations.

Prohibited Concomitant Medications:

The use of niacin or niacin-containing supplements (e.g., multivitamins and energy drinks) is not allowed in the KPT-9274 only cohorts in the Dose Escalation or Expansion Phases. However, for patients in these cohorts that have cleared DLT in cycle 1, niacin ER (up to 2,000 mg co-administered with KPT-9274) may be used as supportive care in an attempt to offset potential side effects (e.g. anemia, arthralgias, myalgias, etc.) of KPT-9274. Prior to initiating niacin ER, patient symptoms and laboratory values should be reviewed and discussed with the Medical Monitor for this study.

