In Part C, a cohort of patients with melanoma that have progressed on an anti-PD1 or anti-PD-L1 antibody will be treated with KPT-9274 (at a dose that cleared DLT evaluation in Part A) + nivolumab. Two dose levels of KPT-9274 (30 and 40 mg) in combination with nivolumab will be tested in parallel. Patients will be enrolled first into the 30 mg cohort. Patients will be treated with 30 or 40 mg KPT-9274 three times a week every other day (Days 1, 3, 5, 8, 10, 12, 15, 17, 19, 22, 24, and 26) during each 28-day cycle in combination with a standard dose and schedule of nivolumab (480 mg on Day 1 of each 28-day cycle). A maximum of 10 patients may be enrolled at each dose level. Treatment will continue until disease progression, unacceptable AEs or toxicity that cannot be managed by supportive care, patient's withdrawal of consent, Investigator decision to discontinue study treatment, pregnancy, death, or Sponsor decision to terminate the study. A safety review committee will evaluate all available data from both cohorts after the last patient enrolled has been observed for at least 2 cycles to determine the RP2D.

Additional dose levels (20 mg or 60 mg) might be evaluated if an optimal dose is not identified and the safety review committee is in agreement. The definition of a DLT is the same as described in Parts A and B. Response will be assessed every 8 weeks per RECIST 1.1 criteria ([Appendix 4](#)).

All phases of the study will be comprised of Screening, Treatment, and Follow-up periods.

Screening will be performed within 30 or 14 days prior to the start of therapy (i.e., Day -30 to Day -1, Day -30 to Day -14, or Day -14 to Day -1), as summarized in [Table 1](#) and [Table 5](#). During the Treatment period, procedures are to be performed during clinic visits prior to the administration of study treatment on those days as presented in [Table 1](#), [Table 2](#), [Table 5](#) and [Table 6](#). The Follow-up period includes the EOT visit, the Safety Follow-up visit, and Durability of Response and Survival Follow-up; see [Table 3](#) and [Table 7](#) for assessments to be completed during the Follow-up period.

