6.1.2. Niacin ER (Part B)

Patients enrolled in Part B of the Dose Escalation Phase or in the Dose Expansion cohort with co-administration of niacin will also receive 500 mg of any FDA approved prescription, generic niacin ER for oral use co-administered with each dose of KPT-9274. The starting dose of 500 mg niacin ER may be titrated up to 2,000 mg of daily dose, per label. A list of approved generic niacin ER will be provided in the Pharmacy Manual. The niacin ER study treatment will be obtained by the site pharmacy.

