# 3.3. CONCOMITANT MEDICATIONS AND PROCEDURES

Concomitant medication consists of any prescription or over-the-counter preparation, including vitamins, dietary supplements, over-the-counter medications, and oral herbal preparations taken during the study, as well as changes in medication. Patients may continue their baseline medication(s). Concomitant medications include any medications used to treat symptoms, concomitant diseases such as diabetes, hypertension, etc., AEs and intercurrent illnesses that are medically necessary as part of standard care. All concomitant medication(s) must be reported on the eCRF. Any diagnostic, therapeutic, or surgical procedure performed during the study period should be recorded, including the dates, description of the procedure(s), and any clinical findings, if applicable. Concomitant medication will generally be summarized among mITT and safety populations, unless otherwise specified.

All medications will be coded using the World Health Organization Drug Dictionary Enhanced (WHO DDE).

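### The niacin ban does not reach Part C in Cycle 1, and the texts disagree on adding niacin ER there from Cycle 2, although the Part C dose decision draws on both periods

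*Protocol*

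**What the plan says.** **Cycle 1.** Protocol 6.9.3 states that niacin or a niacin-containing supplement "is not allowed in cycle 1 of the Part A KPT-9274 only cohorts in the Dose Escalation or Expansion Phases". The synopsis (Prohibited Concomitant Medications) bars it in KPT-9274-only cohorts. Section 6.9.2 gives a general permission for medication that is not on the prohibited list, with one carve-out: "excluding herbal supplements, dietary supplements), deemed necessary for the care of the patient is permitted during the study". Section 6.1.2 describes the niacin ER used in the study as "any FDA approved prescription, generic niacin ER for oral use". SAP 3.3 adds that patients may keep taking their baseline medications.

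**From Cycle 2.** The synopsis (Supportive Care) reads: "For patients in Part A, the addition of niacin ER (up to 2,000 mg daily dose, per label) is allowed". Section 6.9.3 gives the same allowance to the cohorts that it has just named, after discussion with the Medical Monitor. Section 6.9.1 reads "The addition of niacin ER (up to 2,000 mg daily dose, per label) will be allowed after completion of the DLT period" and 6.9.2.1 reads "The addition of niacin ER (up to 2,000 mg daily dose, per label) is allowed after completion of the DLT period"; neither names a Part. Section 6.9.2.1 ends by sending Part C to the nivolumab label for permitted medications and says nothing further on niacin there.

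**The Part C decisions.** Under 6.2.6.1, three patients start at 30 mg, and the dose goes to 40 mg if none has a DLT in Cycle 1. Under 3.1, a safety review committee looks at the data from both cohorts "after the last patient enrolled has been observed for at least 2 cycles to determine the RP2D".

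**The concern.** Protocol 1.2 says that supplemented niacin can relieve adverse events of NAMPT inhibition where tissue expresses NAPRT1, and Part B is built on that idea. Niacin is therefore a known tolerability modifier in this trial. The primary objective of Part C (2.1.1) is the safety, tolerability and RP2D of KPT-9274 + nivolumab, without niacin. If some Part C patients take niacin and the review does not separate their data, the committee may be judging a three-drug regimen in those patients while naming a dose for two drugs.

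The gap looks like an oversight. Section 6.9.3 still bars anticancer agents other than KPT-9274, although Part C gives nivolumab. The prohibited list appears not to have been adapted when Part C was added.

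**Working it through.** The point is mainly a comparison of texts. The plan gives no figure for niacin use or effect in Part C.

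**Step 1. Which rule reaches Part C?**

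| Place in the protocol | Cycle 1 | From Cycle 2 | Reaches Part C? |
|---|---|---|---|
| Synopsis, Prohibited Concomitant Medications | Bars niacin in KPT-9274-only cohorts | Niacin ER allowed in those cohorts after clearing DLT | No |
| Synopsis, Supportive Care | No separate rule | Niacin ER allowed for Part A | No |
| 6.9.3 | Bars niacin in Part A KPT-9274-only cohorts | Niacin ER allowed in those cohorts | No |
| 6.9.2 | Permits medication not prohibited, except supplements | Same | Yes, study-wide |
| 6.9.1 and 6.9.2.1 | Adding niacin ER must wait for the end of the DLT period | Niacin ER allowed, no Part named | Can be read either way |

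Two results follow. In Cycle 1 of Part C, supplements fall outside the permission. If 6.9.1 and 6.9.2.1 apply to Part C, niacin ER may not be newly added either. Prescription niacin already in use is caught by no rule. From Cycle 2, a site that follows the synopsis finds no allowance for Part C, and a site that follows 6.9.1 finds one.

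**Step 2. Which data enter the decision?** The last patient must be observed for at least 2 × 28 = 56 days. The DLT period is the first 28, so at least 56 − 28 = 28 days of that patient's data lie after it. Earlier patients contribute more.

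**Step 3. Would the analysis show it?** SAP 3.4 reports niacin exposure separately, and SAP 5.1.2 has a causality category for niacin. Safety outputs are by part and cohort (SAP 5), and no subgroup analysis is planned (SAP 2.8). Nothing relates a Part C event to the date on which niacin was started.

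**Step 4. Direction only, on assumed rates.** Protocol 9.8 gives one operating characteristic for the 3+3 rule: a probability of 0.57 of halting at a true DLT rate of 33%. It reproduces: 1 − [(1−p)³ + 3p(1−p)² × (1−p)³] = 0.566 at p = 0.33 and 0.572 at p = 1/3.

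Take p = 0.33 for the first three Part C patients. P(at least one DLT) = 1 − 0.67³ = 0.70. Suppose, as an assumption, that niacin lowers a patient's DLT risk to q.

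| q | All three on niacin: 1 − (1−q)³ | One of three on niacin: 1 − 0.67² × (1−q) |
|---|---|---|
| 0.25 | 0.58 | 1 − 0.4489 × 0.75 = 0.66 |
| 0.20 | 0.49 | 1 − 0.4489 × 0.80 = 0.64 |
| 0.10 | 0.27 | 1 − 0.4489 × 0.90 = 0.60 |

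The 33% is far above what has been seen so far. Protocol 1.2.1 reports 2 DLTs in 47 patients (4.3%), without nivolumab. At that rate, P(at least one in three) = 1 − (45/47)³ = 0.12. Even if niacin removed all DLT risk in one of the three patients, it would fall only to 1 − (45/47)² = 0.08. The direction is clear, but the documents do not fix the size.

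**The case against.** The case against is substantial, and much of it stands.

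- **The Cycle 1 gap is narrow.** Supplements are excluded, and 6.9.1 and 6.9.2.1 imply that niacin ER should not be added before the DLT period ends. What remains is a melanoma patient already on prescription niacin. The SAP sentence on baseline medication describes data and does not instruct sites. The Medical Monitor reviews eligibility before C1D1 (4.6), and a detailed medication history is taken (7.5.1.5), so such a patient would be visible. But being visible is not being ruled out: no text tells the site or the monitor to stop the drug.
- **Part A allows the same thing after Cycle 1.** A reader might infer that Part C is uniquely exposed because its RP2D review runs past Cycle 1. The documents do not support that contrast. The synopsis gives Parts A and B the same primary safety endpoints with no Cycle 1 limit. Only their MTD is tied to Cycle 1, and their RP2D rests on safety and tolerability data (2.1.1).
- **A ban through Cycle 2 might seem the natural remedy.** It would withdraw a supportive-care option that Part A keeps. It would not close the gap either, because the committee also sees later cycles of earlier patients. A flag does that without a ban.
- **A reader might try to size the effect from Table 11.** Grade 3 or 4 anemia occurred in 22 + 1 = 23 of 47 patients (48.9%). That count pools doses from 10 to 100 mg, two schedules and 3 + 4 + 10 + 6 + 1 = 24 patients given niacin ER by cohort. Uptake and effect in Part C would have to be invented, and an anemia that prompts niacin has already been counted. No expected shift can be derived from it.
- **A reader might also argue that niacin would undo efficacy in NAPRT1-positive melanoma.** Protocol 1.2 plans niacin for patients with or without NAPRT1, and the Part C rationale (1.3.3) rests on PAK4 and β-catenin. The documents do not say that niacin reverses that mechanism.

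**Conclusion.** The point holds in a limited form. No rule bars prescription niacin already in use during the Part C DLT cycle. From Cycle 2, the texts conflict on whether niacin ER may be added in Part C. Both periods feed the Part C dose decision, and nothing planned separates safety data gathered after a niacin start. Niacin use could therefore make KPT-9274 + nivolumab look better tolerated than it is.

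The size is unknown, because the documents give no human effect size for niacin and no expected number of Part C users. The conclusion rests on the protocol's own statement that niacin can relieve the drug's adverse events, and on at least one Part C patient taking it. A reader might infer that the Part C RP2D will be set too high. The documents do not show that; they show only that the plan would not reveal it. This is a cheap improvement, not a flaw that undermines the trial.

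**What to change.** 1. In the synopsis and 6.9.3, extend the Cycle 1 prohibition of niacin and niacin-containing supplements to Part C.
2. In the synopsis, 6.9.1, 6.9.2.1 and 6.9.3, apply the Part A rule to Part C from Cycle 2: niacin ER may be added only after the DLT period and after discussion with the Medical Monitor.
3. For the Part C RP2D review, flag by dose level the AEs, dose reductions and discontinuations that occur after any niacin start.

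The cost is a sentence in four places and one flag in a listing. No new data are needed: concomitant medications are already recorded on the eCRF (7.5.1.5), and niacin exposure is already in SAP 3.4. A Part C patient on prescription niacin would have to stop it before C1D1 and stay off it for Cycle 1. If Part C enrollment is already complete, the flag alone still helps to interpret the RP2D.
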